Aim 3: Determine the influence of the VAST overall and VAST+ on antibiotic use at each VAMC. The primary outcome measure will be overall rates of antibiotic use. Secondary outcomes will be changes in the rates of broad-spectrum antibiotic use and antibiotic starts, and in length of antibiotic therapy. We anticipate that antibiotic use will decrease after VAST implementation at study sites and compared to VASTs that do not (VAST-), VASTs who receive Antibiotic Use Reports (VAST+) will achieve greater reduction in overall antibiotic use, and specifically in broad-spectrum antibiotics.

Relevance to Veterans and the VA

Veterans experience many of the risk factors associated with development of antimicrobial resistant and healthcare-associated infections. The unprecedented effects of the novel Coronavirus disease 2019 (COVID-19) on the health of our Veterans and on our entire healthcare system makes the demand for ID expertise even more apparent, especially in long-term care. Also, this study directly addresses the VA MISSION ACT to improve access to care, timeliness and quality of care, using telehealth services. Finally, this project is aligned with the priorities of our operation partners: VA Antimicrobial Stewardship Taskforce (ASTF), the VA National Infectious Disease Service (NIDS), VA Pharmacy Benefits Management (PBM) Services, and the Office of Rural Health.

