1. The first metric, days of antibiotic therapy per 1000 days of care (DOT/1000 DOC), measures the overall rate of antibiotic use and is a common metric that accounts for dose adjustments, including for people who receive dialysis. Administration of any dose of an antimicrobial on a given day represents a single DOT for that agent, regardless of the number of times the doses are administered or the dose strength.
2. Second, we will specifically examine the rate of broad-spectrum antibiotics, defining broad-spectrum agents as those with an Antibiotic Spectrum Index (ASI) score of ≥ 8 . This scale ranges from 1 to 13.
3. The third metric is the rate of antibiotic starts (new prescriptions), calculated as the number of starts per 1000 DOC.
4. The fourth metric is the length of antibiotic therapy in days.
 - a. For people on hemodialysis, up to 72 hours may occur between doses of specific agents (e.g. vancomycin, aminoglycosides, several cephalosporins); these will be considered as a single course.

For each site, we will calculate these statistics at monthly intervals for the 12 months prior to and the 15 months following the first VAST session, allowing for a 3-month wash-in period, to generate descriptive summaries of changes in acute care and in long-term care over time, understand month-to-month variability in these metrics, and to flag any issues with data availability or validity in the course of the

intervention given operational shifts occurring at facilities around COVID-19 treatment or the rollout of the Cerner electronic medical record across the VA.

Additionally, we will use CDW data to determine the antibiotic prescribing patterns for respiratory tract infections and urinary tract infections (UTI) at VAST sites beginning January 1, 2019. We will then conduct a thorough medical record review on patients identified using CDW. Using this data, we will explore system factors, including prescriber specialty, to predict the rate of prescribing of antibiotics by race and ethnicity.

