5.6 Data Analysis

1. VAST Implementation

The primary research team will assess qualitative aspects of implementation and sustainability. With each facilitation call, whether scheduled or ad hoc, members of the primary research team will use field notes to log barriers and facilitators related to implementation. The research team will use process maps to record adaptations. Changes from the initial map will be categorized as major or minor. Further, the number of weeks each VAST required to achieve their final process map will be noted. Together, these assessments will be used to assess fidelity of implementation and to transform the Implementation Guide into a final, robust Implementation Playbook.

2. Staff Perceptions

Once the intervention period for all VASTs is complete, we will assess for differences in the VAST- vs VAST+ arms on perceived influences on Veteran care, proportion of VAST recommendations accepted, and the user experience survey.

3. Evaluation of clinical activities

Characteristics of each facility including number of beds, number of CLC beds, medical complexity group, attendance of leadership at VAST sessions and the mean number of cases discussed per session will also be compared. If significant differences are seen between VAST- and VAST+ sites, additional multivariable analyses will be conducted.

4. Facility-Level Antibiotic Use

To assess for impact of VAST on antibiotic use, we will summarize the 4 antibiotic use metrics for each site, comparing the pre- and post-implementation periods for the acute and long-term care units. Rates of overall antibiotic use (DOT/1000 DOC), broad-spectrum antibiotic use (DOT/1000 DOC) and antibiotic starts (new prescriptions/1000 DOC) will be calculated with 95% confidence intervals based on exact Poisson distributions. To summarize length of therapy in the pre- and post-implementation periods, we will calculate means and 95% confidence intervals.

To assess for differences between the VAST- and VAST+ study arms, we will use a multi-level Poisson regression model in which facilities will be

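### Exact Poisson confidence intervals for the two days-of-therapy rates ignore multi-day courses and are too narrow, by a factor that depends on a course length the documents do not give

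*Combined protocol and SAP*

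**What the plan says.** Section 3.0 (Aim 3) names the primary outcome: "The primary outcome measure will be overall rates of antibiotic use". Section 5.5 (Facility-Level Antibiotic Use) measures it as DOT per 1000 days of care (DOC) and defines the count: "Administration of any dose of an antimicrobial on a given day represents a single DOT for that agent". The broad-spectrum metric uses the same count, restricted to agents with a high spectrum score. Starts are different, being "calculated as the number of starts per 1000 DOC", so each new prescription counts once.

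The same section recognises that treatment comes in courses of several days. "The fourth metric is the length of antibiotic therapy in days", and widely spaced doses in people on haemodialysis are not split: "these will be considered as a single course".

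For the analysis, section 5.6 says "we will summarize the 4 antibiotic use metrics for each site, comparing the pre- and post-implementation periods", separately for acute and long-term care, with the stated purpose of gauging the impact of VAST. The three rates "will be calculated with 95% confidence intervals based on exact Poisson distributions". Nothing in the documents allows for overdispersion or clustering by course or patient in these intervals, or provides a robust variance or a bootstrap.

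The comparison of arms is a separate analysis: "we will use a multi-level Poisson regression model in which facilities will be" random effects, with the arm-by-time interaction as the effect of interest.

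**The concern.** An exact Poisson interval is exact only if the counted events are independent, so that the variance of the count equals its mean. DOT are not independent. Once a patient starts a seven-day course of one agent, seven counts follow from one decision; a second agent given on the same days doubles them. The effective number of independent events is nearer the number of courses than the number of DOT.

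The intervals would therefore look more precise than the data allow, on the primary metric, at every site and in both settings. A site team or reader who compares the pre and post intervals could take ordinary variation in the number and length of courses for an effect of VAST, in either direction. With up to 10 sites, 2 settings and 2 DOT metrics, there could be 10 × 2 × 2 = 40 such pairs of intervals.

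**Working it through.** The plan states no DOT count, rate, course length or interval width, so there is no figure to reproduce. The check is how far the specified method departs from nominal under stated assumptions.

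**Inputs from the documents.** Exact Poisson limits at 95% (section 5.6); one count per agent per day (section 5.5); courses lasting several days (section 5.5).

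**Assumed inputs.** Mean DOT per course *m* from 2 to 14, with coefficient of variation (CV) 0.5, so SD is half the mean. CV 1 is shown as a harsher case.

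**Model.** Courses arrive as a Poisson process and each adds *L* DOT. Then

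- variance/mean of total DOT: φ = E[L²]/E[L] = m(1 + CV²);
- factor by which the Poisson interval is too narrow: √φ;
- actual coverage of a nominal 95% interval: 2Φ(1.96/√φ) − 1;
- chance that the pre and post intervals fail to overlap with no true change and equal expected counts: 2[1 − Φ(2 × 1.96/√(2φ))]. The interval half-widths add to 2 × 1.96√μ, where μ is the expected count in each period, while the difference has SD √(2φμ).

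For m = 7 and CV = 0.5: φ = 7 × 1.25 = 8.75 and √φ = 2.96. Coverage is 2Φ(1.96/2.96) − 1 = 49%. Non-overlap is 2[1 − Φ(3.92/√17.5)] = 2[1 − Φ(0.937)] = 35%.

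| Mean DOT per course | CV | φ | Times too narrow | Coverage | Non-overlap, no true change |
|---|---|---|---|---|---|
| 1 (independent events) | 0 | 1 | 1.0 | 95% | 0.6% |
| 2 | 0.5 | 2.5 | 1.6 | 78% | 8% |
| 3 | 0.5 | 3.75 | 1.9 | 69% | 15% |
| 7 | 0.5 | 8.75 | 3.0 | 49% | 35% |
| 14 | 0.5 | 17.5 | 4.2 | 36% | 51% |
| 7 | 1 | 14 | 3.7 | 40% | 46% |
| 14 | 1 | 28 | 5.3 | 29% | 60% |

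**Check by simulation.** With 4,000 replicates and exact chi-square limits, m = 7 and CV = 0.5 gave a width ratio of 0.344 (1/0.344 = 2.9 times too narrow) at both 1,000 and 5,000 expected DOT, with coverage of 49% and 51%. With one-day courses, coverage was 95%. More data therefore do not cure the fault.

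**Starts.** Each course counts once, so φ from course length is 1 and this argument does not apply.

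**The case against.** The strongest reply concerns use. These are descriptive per-site summaries, the intervals sit on single rates rather than on the pre/post contrast, and the plan attaches no test, threshold or overlap rule to them. The central hypothesis, that feedback reports add to VAST, is examined in the multi-level model. This stands. A reader might infer that the plan declares site-level significance from these intervals, or that the randomised comparison is invalid because of them; the documents support neither. Whether the Poisson model itself allows for overdispersion is a related question, but it concerns a different sentence of the plan.

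The second reply is that the size is unknown. This also stands. A reader might take a figure such as one third of the proper width as established. That needs φ = 9, for example a fixed 9 DOT per course, and the documents give no mean or SD for length of therapy. Course length may differ between acute and long-term care and between overall and broad-spectrum use. Because administrations are attributed to specific units, days after a patient leaves a unit may not count there, which would shorten counted courses. Concurrent agents and repeat courses work the other way.

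Neither reply rescues the method. The direction follows from the plan's own definition of DOT, and even a two-day mean leaves coverage near 78%. The stated purpose of the summaries is to assess VAST's impact, and readers will compare the intervals whether or not a rule says so.

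**Conclusion.** The concern holds for overall and broad-spectrum DOT/1000 DOC. Exact Poisson limits are the wrong method for these two rates, and nothing in the documents corrects for it. It does not extend to antibiotic starts, although the quoted sentence covers them too; starts may still cluster by patient or month, but the documents give nothing to size that.

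The direction is certain. The size is conditional: for assumed mean courses of 2 to 14 days with SD half the mean, the intervals are about 1.6 to 4.2 times too narrow. Under the same assumptions, chance alone would separate the pre and post intervals in about 8% to 51% of comparisons, against 0.6% for truly independent events. The model takes courses as independent and ignores trend.

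This is a should-fix. It affects the primary metric, but in per-site pre/post summaries without a formal test, and not in the VAST- versus VAST+ comparison.

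**What to change.** For the two DOT rates, replace the exact Poisson limits in section 5.6 with dispersion-scaled intervals (quasi-Poisson or robust) from the monthly values already planned in section 5.5. Twelve months before the first session, and 15 − 3 = 12 after the wash-in, leave about 11 degrees of freedom per period for a single rate, so use t rather than normal limits.

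Where the extract carries a course identifier or a de-identified patient identifier, a bootstrap of courses or patients within site, setting and period is an alternative. The plan does not establish that it will: sections 5.1 and 7.0 say that facility-level data are stripped of identifying information before extraction and that only the setting is noted. Confirm this before choosing the bootstrap.

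Report the pre/post rate ratio for each site and setting with the same type of interval, so that readers need not judge change by overlap. Keep Poisson limits at most for starts, described as an approximation.

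The monthly option needs no new data, only a short change to the analysis text and code. The intervals will be wider, and monthly scaling also absorbs trend and the operational shifts that section 5.5 mentions (COVID-19 and the change of electronic record), so some of the extra width will not come from course clustering. The text should say so.

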5.0 Study Procedures

5.1 Study Design

We will conduct a Type 2 hybrid effectiveness-implementation design [37], randomizing rural VAMCs that do not have ID-trained professionals on staff to implement the VAST alone (VAST-) versus VAST + antibiotic use feedback (VAST+). We propose to test the implementation strategy, specifically assessing modification and adaptations and effectiveness, measured as the VAST's influence on Veteran care and on antibiotic use.

The 4 main activities of the study are

1. Determine modifications of **VAST implementation** through ongoing discussions with champions at the intervention sites and with the infectious disease experts.
2. Assess **staff perceptions** of the VAST using surveys and semi-structured interviews to gather qualitative data about what key VAST members perceive as facilitators, barriers and burden to VAST implementation.
3. Evaluate the **clinical activities** of each VAST. This evaluation will include using chart review to describe the patients discussed, including their clinical diagnoses, as well as acceptance of recommendations by providers. These activities will involve use of the VA's administrative databases as well as chart review.
4. Measure changes in overall **facility-level antibiotic use** for each VAST. These activities will involve extraction of antibiotic use and census data from the VA's administrative databases

Study Population

The study will include up to 10 intervention sites, which are rural VA facilities. Infectious disease experts will serve as Local Site Investigators (LSIs). Each LSI will work with at least 1 intervention site (rural VA facility) to set up a VAST.

1. VAST Implementation

For this study activity, study participants will include the participating sites.

2. Staff perceptions

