5.5 Study Evaluations

1. VAST Implementation

Randomization

To randomize rural VAMCs, we will use a matched pairs design to ensure that the total number of acute and long-term care beds is similar between the two study arms. For simplicity, if more than one rural VAMC forms a VAST with the same off-site ID expert, (e.g., both Altoona and Erie have a relationship with the Pittsburgh VAMC) we will randomize both rural VAMCs into the same arm.

VAST Members & Activities

Staff from acute (hospital) and long-term care (CLC) units will populate the team, with the intent of using more than one person with the same role to allow for fluidity among individual members. Each VAST will identify 2 to 3 champions, likely pharmacists and infection preventionists, with responsibilities that include identifying patients prescribed antibiotics and recording the VAST's recommendations in the electronic medical record. Contributions of the ID physician will include his or her clinical knowledge and experience with antimicrobial stewardship. The ID physician will identify 1-2 other individuals, such as an ID-trained clinical pharmacist, to also participate in the VAST. This will enhance continuity of the VAST during holidays, vacations, and travel. Each team will also include a field research assistant for the ID expert(s); field research assistants will help support VAST implementation and data collection.

The VAST will meet for one hour each week. As a whole, team members from the rural VAMC and off-site ID experts will participate in chart review, discussion, and making recommendations regarding the need and choice of antimicrobial agent(s), length of therapy, orders for and interpretation of microbiological cultures and diagnostic tests. At each session, the field research assistant will note the names, roles, and practice setting for each of the VAST participants; this information will be shared with the primary research team.

When feasible, the ID expert(s) will travel to the rural VAMC for a face-to-face kickoff meeting. This will facilitate team building and help set the tone for the ensuing videoconferences. Leadership support to allow time for personnel from the rural as well as the ID expert(s) VAMCs to actively engage in the VAST will be a key factor for success. Further, the presence of Chiefs or Assistant Chiefs of Staff, Medicine, Nursing, and Pharmacy from the rural VAMC, especially at the first 4 to 8 VAST sessions, will help engage other clinical staff.

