parameterized as random effects and study arm and time (year before vs. year of implementation) as fixed effects, with their interaction as the estimated effect of interest. This model will yield estimated rate ratios for overall antibiotic use, use of broad-spectrum agents (ASI ≥ 8), and antibiotic starts for each intervention arm. Length of therapy can be modeled as continuous outcomes in similarly parameterized models, with the interaction of arm and study year as the effect of interest.

Qualitative data will be analyzed in aggregate by the research team for each study activity and shared with the primary research team. We will use data describing specific goals or objectives for the VAST to assess our hypothesis.

Additionally, we will summarize and compare patient characteristics for patients with RTI or UTI. For patients in this cohort, we determine provider and facility factors that are predictive of over, under, or guideline-concordant prescribing for each diagnosis. Information collected from the CDW will be used to develop and pilot a natural language processing algorithm that detects UTIs using provider documentation. This algorithm will be developed using medical record note text stored in the CDW.

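### The planned Poisson model for VAST+ versus VAST- lets facilities differ in level but not in change, so the standard error of the arm-by-time effect is too small whenever sites change unequally or antibiotic-days are overdispersed

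*Combined protocol and SAP*

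**What the plan says.** Section 3.0 (Aim 3) states that "The primary outcome measure will be overall rates of antibiotic use", measured in section 5.5 as DOT per 1,000 days of care. For the randomised comparison, section 5.6 (Facility-Level Antibiotic Use) plans a "multi-level Poisson regression model in which facilities will be" treated as random. Arm and a two-level time variable, contrasting the year before with the implementation year, enter as "fixed effects, with their interaction as the estimated effect of interest". The same model serves broad-spectrum use and antibiotic starts. Length of therapy gets a similarly built model for a continuous outcome.

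Section 5.1 sets the size: "The study will include up to 10 intervention sites". On allocation, section 5.5 says "we will use a matched pairs design to ensure that the total number of acute and long-term care beds is similar" in the two arms, and it places rural sites that share an off-site ID expert in the same arm. Section 5.5 also defines the count: "Administration of any dose of an antimicrobial on a given day represents a single DOT for that agent".

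Time appears only as a fixed effect. The available text names no facility-by-period random effect, overdispersion parameter, robust variance, small-sample degrees of freedom or randomisation-based test. It also gives no alpha or sidedness for the interaction.

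**The concern.** The randomised units are facilities, or groups of facilities sharing an expert, and there are at most 10. The arm-by-time effect contrasts facility-level changes, so its error must include how much true change varies from one facility to another. A random facility level does not supply this. It removes differences in level and then assumes that every facility in an arm has the same true before-after ratio and that counts have variance equal to their mean.

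The plan's own text makes both assumptions doubtful. Section 5.5 foresees operational shifts at facilities from COVID-19 and the electronic record rollout, but uses the monthly series only for description and data checks. Section 5.5 also expects each site to adapt the intervention. Each agent-day counts as one DOT, so one course contributes several linked counts.

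At stake is the only specified analysis of the randomised comparison on the Aim 3 primary outcome. Ordinary differences between sites in year-on-year change could be read as an effect of the Antibiotic Use Report.

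**Working it through.** The available text gives no sample-size or power figure for this comparison, so there is none to reproduce.

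**Inputs from the documents:** up to 10 facilities (5.1), taken as k = 5 per arm because allocation is in matched pairs (5.5); a two-level time variable and a facility random effect (5.6).

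**Assumptions, not in the documents:** two-sided 5% test; μ = 500 to 8,000 DOT per facility-year; SD of facility log change τ = 0 to 0.10; no true effect; independent facilities.

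**Formulas.** The facility level cancels from the interaction, so for the log ratio of rate ratios:

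- model variance ≈ 4/(kμ)
- true variance ≈ 4/(kμ) + 2τ²/k
- true/model variance = 1 + τ²μ/2, which does not depend on k
- false-positive rate ≈ 2[1 − Φ(1.96/√(1 + τ²μ/2))]

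**Example, μ = 2,500.** Model SE = √(4/12,500) = 0.018.

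- τ = 0.05: variance ratio 1 + 0.0025 × 1,250 = 4.125. True SE is 2.0 times the model SE, about 0.036. False-positive rate 2[1 − Φ(0.965)] = 33%.
- τ = 0.10: variance ratio 1 + 0.01 × 1,250 = 13.5. True SE is 3.7 times the model SE, about 0.066. False-positive rate 2[1 − Φ(0.533)] = 59%.

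**Results.** Each cell gives the closed form, then a simulation of 20,000 null trials (SD of facility level 0.3, Wald test from arm-period totals):

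| DOT per facility-year | τ = 0 | τ = 0.02 | τ = 0.05 | τ = 0.10 |
|---|---|---|---|---|
| 500 | 5% / 5% | 6% / 6% | 12% / 13% | 29% / 32% |
| 2,500 | 5% / 5% | 11% / 12% | 33% / 36% | 59% / 61% |
| 8,000 | 5% / 5% | 22% / 24% | 55% / 57% | 76% / 77% |

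**Direct fits** of the random-intercept Poisson model at τ = 0.10 agree in direction. One gave 63% rejection (3,000 DOT, 150 trials), where the simulated Wald test gives 64%. Another gave 69% (2,500 DOT, 200 trials) against 61%. That second gap is about 2.3 Monte Carlo standard errors (8 points over √(0.61 × 0.39/200) = 3.4 points), so the exact figure is uncertain but the inflation is not.

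**Overdispersion alone** (τ = 0, variance φ times Poisson): the rate is 2[1 − Φ(1.96/√φ)], which is 17% at φ = 2, 33% at φ = 4 and 49% at φ = 8.

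**Would a per-facility analysis be enough?** A two-sample t-test on facility log changes holds about 5% in every setting above, but those settings treat facilities as independent. Suppose two expert-sharing pairs of sites sit in each arm, with within-pair correlation of change 0.3 to 0.8 (assumed), τ = 0.10 and 2,500 DOT. The same t-test then rejects about 8% to 14% of the time.

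**The case against.** The strongest reply is that section 5.6 is a short summary. It does not say intercept-only, does not rule out a facility-by-period term or a dispersion parameter, and does not name a Wald test. It presents the interaction as something to estimate, with no alpha or decision rule. This stands in part: the 5% test is an assumption here, and without a test the same fault appears as intervals that are too narrow. It does not remove the point. Time is listed only as fixed, and an analyst following the text would fit a random level.

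A reader might infer that false positives far exceed 5% whatever the data look like, or that intervals are always several times too narrow. The documents support neither. They give neither τ nor DOT volume. At 500 DOT with τ between 0.02 and 0.05 the rate is about 6% to 13%, and the true SE is at most about 1.3 times the model SE. Section 5.5 supports unequal change but not its amount.

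A reader might also infer that a t-test on one value per facility settles the matter. It does not, because section 5.5 randomises sites sharing an expert together.

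Three other replies fail. Fitting monthly rows does not help, because with a two-level time variable the interaction still rests on period totals. More sites do not help, because the variance ratio does not depend on k. Matching on beds balances size, not change over time.

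**Conclusion.** The concern holds in conditional form. On its plain reading, the stated model gives the arm-by-time effect a standard error set by day counts, which is correct only if all facilities in an arm change identically and DOT behave as independent Poisson events. Under the assumptions listed, the false-positive rate runs from about 6% (500 DOT, SD 0.02) to 77% (8,000 DOT, SD 0.10). At 2,500 DOT the true SE is about 2 to 4 times the model SE for SDs of 0.05 to 0.10. Little variation is needed: the closed form reaches 10% at an SD of 0.041 with 500 DOT, or 0.017 with 3,000. This should be corrected before comparative results are seen, because it affects the only specified analysis of the randomised contrast on the primary outcome.

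**What to change.** Make the primary analysis a comparison between arms of log(post rate/pre rate), with one value per randomised unit and sites that share an ID expert pooled into one unit. Use a t or permutation reference whose degrees of freedom come from the number of randomised units and which respects the matched pairs. If there are only five pairs, within-pair permutation has 2⁵ = 32 assignments and a smallest two-sided p of 2/32 = 0.0625, so it could not reach 5%. A paired t-test would have 5 − 1 = 4 degrees of freedom. The choice should be made knowing this.

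Alternatively, keep the regression and add facility-by-period and shared-expert-by-period random effects, a dispersion term and small-sample degrees of freedom. State the alpha and sidedness either way.

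Apply the same approach to broad-spectrum DOT and starts. Length of therapy is continuous, so the Poisson argument does not carry over; use the randomised-unit change, or a unit-by-period random effect, in that model.

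No new data are needed. The cost is precision. At τ = 0.10 and 3,000 DOT, with 10 independent unpaired facilities (8 df), the SE is √(4/15,000 + 0.02/5) = 0.065, against 0.016 under the planned model. The ratio of rate ratios detectable with 80% power is then about 0.81, not the 0.955 that the planned model would suggest. With fewer units or a paired analysis the degrees of freedom fall further.
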